1.5 Azacitidine as a form of immunotherapy

Demethylating agents such as azacitidine and decitabine have various effects on multiple facets of the immune system. In vitro studies of AML and melanoma cells have demonstrated that co-culture with decitabine results in increased class I and II MHC expression (21, 22). Azacitidine administered to patients following allogeneic transplantation has been associated with a concomitant increase in cytotoxic CD8+ T cells and regulatory T cells, potentially resulting in increased GvL without commensurate increase in GVHD (23). Effects on NK cells are mixed: while decitabine has been shown to increase NKG2D-dependent sensitivity of AML cells to NK-mediated killing in vitro (24), azacitidine increases KIR expression (25, 26), and decreases expression of TRAIL, NKG2D, and NKp46 (27).

Azacitidine has been used in patients safely as monotherapy. In a dose-finding study, azacitidine was used as prophylactic / maintenance therapy in heavily pretreated refractory/relapsed AML/MDS patients following allogeneic transplant, and a dose of 32 mg/m² given for 5 days was shown to be safe for at least 4 cycles (28). 1 year EFS in this cohort was 58%. Azacitidine monotherapy has also been studied in AML patients following allogeneic transplantation as pre-emptive therapy for declining CD34 chimerism (RELAZA trial) (29). Azacitidine 75mg/m²/day x 7 days was administered every 28 days in AML patients with declining chimerism post-transplant; of 20 patients, 10 achieved an increase in CD34+ donor chimerism, and 3 of these remained relapse-free for >6 months. Although there is less data for the use of demethylating agents in ALL, there is preclinical evidence that they may be effective (30), and there is early clinical indication that they may be effective in a subset of these patients (31).

1.6 Use of azacitidine with DLI as immunotherapy in patients with leukemic relapse

Azacitidine has been administered safely in combination with DLI for patients with AML relapse 30 days to 4 years post-transplant (32). The combination was shown to be active, inducing CR in 7 of 30 patients, with no increased risk of GVHD or azacitidine toxicity. Decitabine has also been used for relapse in 14 ALL, AML, and CML patients following transplant. High doses of 100-150 mg/m² Q12h x 5 days followed by DLI resulted in a response in 57% of patients, including one of two ALL patients (33). In addition, a lower (hypomethylating) dose of 20mg/m² IV x 5 days is also effective in patients with MDS (34).

1.7 Safety of Azacitidine

In the 2010 Phase I study of azacitidine used post-transplant in 45 very-high risk patients, the drug was well-tolerated at a maximum dose of 40mg/m²/day x 5 days (28). In terms of hematologic toxicity, there was no correlation between white blood cell or platelet count at the start of maintenance and development of hematologic toxicities. They observed reversible grade 1-2 or 3 thrombocytopenia (n = 7 and n = 2), and in 1 of 2 patients receiving 40 mg/m². Grade 1-2 neutropenia was documented in 7 cases.

Other toxicities included: Grade 1 nausea (n = 9), Grade 2 fatigue (n = 6), Grade 1-2 transaminases elevation (n=3), Pruritus (n=1), cholecystitis (n=1), grade 1 confusion (n =2), grade 2 creatinine elevation (n = 1), oral ulcers (n = 2). There were also 3 cases of possible ocular toxicity: conjunctival erythema; retina hemorrhage with platelet count drop to 50,000/mm³ (possibly pre-existing); and papilledema.

The most serious possibly drug-related adverse event was 1 case of pulmonary hemorrhage because of fungal pneumonia, which occurred in a patient receiving a second HSCT, who evolved with thrombocytopenia and multiorgan failure. Infections that occurred during the treatment period were considered to be within the expected profile seen in this population.

1.8 Use of Azacitidine in Children

Azacitidine has been used safely in children. The maximum tolerated dose was examined in children as early as 1973. Children ages 2 to 17 years were treated with azacitidine monotherapy for 5 days every 14 days. The maximum tolerated dose was 150-200 mg/m² (35). Kalwinsky et al used azacitidine in 68 previously untreated pediatric AML patients at a dose of 300mg/m² on day 4 and 5 in combination with cytotoxic chemotherapy (36). A phase II study in 1996 randomized 41 pediatric patients with refractory disease to receive cytotoxic chemotherapy with or without azacitidine at a dose of 250mg/m²/day x 2 days), with a significantly higher CR rate in the group of children who received azacitidine (37).

1.9 Lineage specific chimerism analysis

Monitoring chimerism in different hematopoietic cell lineages can increase the sensitivity of detecting the minority population when there are lineage differences in the extent of mixed chimerism. Zetterquist et al. showed that monitoring mixed chimerism in B-cell lineage correlated well with molecular confirmation of minimal residual disease and was detectable 2.5 months before morphologic relapse (38). Similarly, Mattson et al. showed that MC in CD13+ and CD33+ cell lineage in patients with AML could detect relapse a median of 66 days before hematologic relapse (39). Our feasibility study confirmed that leukemia-specific lineage mixed chimerism heralds relapse (40).

1.10 Minimal residual disease monitoring of AML in the post-transplant setting

In addition to chimerism analysis in the post allogeneic hematopoietic stem cell transplantation (allo-HSCT) setting, a variety of other high sensitivity methods for quantification of measurable disease burden in AML have been described and have recently been reviewed (10, 41-43), that allow for risk stratification when used prior to allo-HSCT and early prediction of impending

clinically evident relapse when used in surveillance monitoring post allo-HSCT. These high sensitivity measures of AML disease burden may also help quantify the efficacy of post allo-HSCT maintenance interventions (29, 43). The optimal MRD monitoring strategy in AML is a subject of current investigation.

1.11 Preliminary data

Our group has been studying the use of subset chimerism testing and pre-emptive immunotherapy with fast withdrawal of immunosuppression (FWI) and donor lymphocyte infusion (DLI) since 2005. Our prospective multi-institutional study evaluated the feasibility of longitudinal chimerism testing in a central laboratory (including WB, CD3+, and leukemia-specific lineage chimerism) in patients with a variety of hematologic malignancies, and evaluated the feasibility of fast withdrawal of immunosuppression based on WB chimerism results. Centralized chimerism testing was feasible and showed low inter-assay variability. Increasing mixed chimerism (MC) in WB was not useful as a predictor of relapse in our study. The presence of full donor chimerism in WB, CD3+ and leukemia-specific lineages on all measurements was related to a significantly lower risk of relapse than the presence of MC in either subset (11% vs 71%, respectively; P=0.03). Increasing host chimerism in leukemia-specific lineage heralds relapse, but it was not detected early enough to allow immunotherapy. The conclusion of the study was that the goal of preemptive immunotherapy should be to achieve full donor chimerism in WB in CD3+ and leukemia-specific lineages, in an effort to prevent relapse before donor chimerism declines (40).

In a recent prospective UCSF analysis, 43 children (25 AML, 18 ALL,) underwent myeloablative BMT or PBSCT followed by immunomodulatory therapy (IT) between 2009 and 2012 (44). Patients with FDC in BM and PB at day 30 or evidence of GVHD were assigned to observation only (N=12). Patients with mixed chimerism (regardless of MRD) were assigned to intervention. Intervention consisted of fast withdrawal of immunosuppression (FWI) in 26 patients; 14 of these also received DLI. Five patients could not be assigned due to early death or relapse. Overall survival at a median of 30 months was 54%. Toxicity was acceptable, with an acute GVHD rate of 19% in the intervention arm, and a toxic death rate of 4%. Relapse was observed in 10/38 patients; 8 of the 10 relapses occurred in the intervention arm (associated with mixed chimerism). Four of these occurred late at >24 months post-transplant.

The most powerful predictor of post-transplant relapse was BM chimerism in the leukemia-specific subset. Mixed chimerism was associated with a 41% relapse rate, compared to a 6% rate in patients with full donor chimerism (p=0.001). Mixed chimerism in the BM CD34 subset was also significantly associated with increased risk of relapse (38% vs 10%, p=0.04). Interestingly, no patients who demonstrated full donor chimerism in all subsets (CD3, CD34, and leukemia-specific CD3 or CD19) relapsed (0 out of 7 patients), compared to a relapse rate of 37% in patients demonstrating mixed chimerism in any subset (p=0.02).

1.12 Rationale

Our most recent approach to decrease the risk of relapse post-transplant has focused on immunomodulatory therapy including fast withdrawal of calcineurin inhibitor (FWI) and administration of donor lymphocyte infusion (DLI). Our data has demonstrated that FWI with or without DLI administered to patients with mixed chimerism clearly prolongs survival. However, patients who were full donor chimeras remained at risk for relapse if they did not develop GVHD, as they were not eligible for immunomodulatory therapy. Therefore, additional therapy is required for this group of patients with higher risk of relapse.

An attractive option for post-transplant consolidation that has the potential to synergize with immunomodulatory therapy is the administration of a hypomethylating agent such as azacitidine. The main advantages to using this class of agents compared to other agents are:

- They are relatively safe / tolerable, so can be used in patients with recovering organ function post-transplant.
- They are potentially synergistic with immunotherapy, augmenting the Graft versus Leukemia (GvL) effect.
- They may provide protection against GvHD (the primary risk of post-transplant immunomodulation) even while preserving GvL effect.
- They can be applied indiscriminately to most types of AML and other myeloid malignancies (they do not require a specific target, unlike newer “targeted” therapies).

2.0 Objectives

2.1 Primary Objectives

- 2.1.1 To evaluate the efficacy of the risk-adaptive approach to relapse reduction (based on the relapse rate) with a combination of azacitidine and donor lymphocyte infusion (DLI) in pediatric patients with AML, ALL, or MDS treated with stem cell transplantation.
- 2.1.2 To investigate the safety and toxicity of the treatment with a combination of azacitidine and donor lymphocyte infusion (DLI) in pediatric patients with AML, ALL, or MDS treated with stem cell transplantation.

2.2 Secondary / Exploratory Objectives

- 2.2.1 To evaluate the effect of risk-adapted azacitidine and DLI on other outcomes such as relapse-free survival and median time to relapse.
- 2.2.2 To evaluate the effect of post-transplant azacitidine on immune function, including T cell function.
- 2.2.3 To evaluate the feasibility and utility of a gene-expression platform for the detection of minimal residual disease with high sensitivity in AML patients following HSCT.

2.3 Hypotheses

- 2.3.1 In patients with acute leukemia, the use of azacitidine and DLI is associated with a lower rate of relapse at two years compared with historical controls.
- 2.3.2 In patients at high risk for post-transplant relapse, the use of azacitidine and DLI is associated with a low rate of Grade III-IV GvHD or drug-related severe adverse events.

3.0 Study Design and Eligibility Criteria

3.1 Study Design (see also Study Schema, page 3)

- 3.1.1 We propose a Phase II single-arm trial of azacitidine (IV or SC) in combination with escalating donor lymphocyte infusions (DLI). This study will be open to patients with ALL, AML, JMML, or MDS.
- 3.1.2 The first cycle of azacitidine will be administered during withdrawal of immunosuppression for patients not developing severe organ toxicity or Grade III-IV GVHD.
- 3.1.3 After the initial cycle during withdrawal of immunosuppression (duration is based on day 28 PB chimerism), azacitidine is given for 4 days in 6-week cycles (+/- 2 weeks) at a dose of 40 mg/m²/day.
- 3.1.4 For patients meeting High Risk criteria who have available cell product, DLI is given on day 5 of each cycle in escalating doses. Peripheral blood chimerism and MRD is assessed after week 4, prior to initiating the next cycle. BM chimerism and MRD is

obtained at regular intervals prior to specified cycles as per the study schedule. Patients will receive up to 7 cycles as tolerated.

3.1.5 Patients will be followed by laboratory monitoring and physician evaluation prior to each cycle. Weekly labs will be obtained and will include toxicity monitoring (CBC, LFTs, and electrolytes) and correlative studies, such as immunophenotype and T cell function by PHA. Patients will be followed for two years to study toxicity and GVHD outcomes as well as relapse incidence.

3.2 Inclusion Criteria

3.2.1 Patients age 0 – 29.9 years undergoing allogeneic stem cell transplant using a peripheral blood stem cell source.

3.2.1.1 Patients receiving bone marrow or umbilical cord blood as a stem cell source may also be considered for enrollment with acknowledgement that if there is insufficient product available for DLI, the patient will receive azacitidine without DLI per Standard-Risk treatment.

3.2.2 Patients with one of the following diagnoses:

3.2.2.1 Acute myeloid leukemia (AML)

3.2.2.2 Acute lymphoblastic leukemia (ALL)

3.2.2.3 Juvenile myelomonocytic leukemia (JMML)

3.2.2.4 Myelodysplastic syndrome (MDS)

3.3 Exclusion Criteria:

3.3.1 Patients who have had a prior transplant

3.3.2 Patients receiving a haploidentical/T cell depleted transplant

3.3.3 Patients with Fanconi anemia or other cancer-predisposition syndromes

3.3.4 Patients with expected survival <12 weeks

3.3.5 Lansky score <60%

4.0 Patient Registration

4.1 Recruitment:

Patients will be recruited to the study by a bone marrow transplant physician during pre-transplant clinic visits, or during hospital admission. Patients will be consented for study any time between pre-transplant consent conference and day +28; enrollment will occur before day +28 and prior to withdrawal of immunosuppression.

4.2 Registration:

All prospective patients will undergo an informed consent conference during which their transplant physician will explain risks, benefits and alternatives to the study participation. The assent of the recipient will be obtained when age appropriate, as well as parental permission. To register patients, the attending physician will contact the Study Chair, [REDACTED]

[REDACTED] The investigator will complete the eligibility forms (provided in the Case Report Form packet) and fax them per the instructions on the form to either the UCSF PI or UCSF Study Coordinator. Pertinent information will be maintained at UCSF on each enrolled patient.

5.0 Investigational Intervention Plan

5.1 Collection of Patient Demographic Information

5.1.1 Age

5.1.2 Disease type / cytogenetics / genetic risk classification

5.1.3 Disease status at HSCT (site of disease, MRD status at each site)

- Pre-transplant MRD must be collected within 28 days prior to transplant.

5.1.4 Conditioning regimen (Bu/Flu, TBI/Cy, others)

5.1.5 Donor (related versus unrelated)

5.1.6 HLA match

5.1.7 GVHD prophylaxis (use of steroids or other agents; use of calcineurin inhibitor and target; use of serotherapy)

5.2 Schedule of Testing

5.2.1 BM studies to be obtained with each BM exam (not including correlative samples):

- Chimerism:
 - Chimerism <100% in any lineage / cell subset will be designated “Mixed Donor Chimerism” (MDC)
 - Chimerism of 100% in all lineages / subsets will be designated “Full Donor Chimerism” (FDC)
- Morphology
- Minimal residual disease (MRD):
 - Multiparametric flow cytometry, FISH, PCR, or deep sequencing (DS-MRD, Sequentia ClonoSIGHT, Adaptive) should be sent as clinically indicated, but results are not required prior to initiation of next cycle. Preliminary risk stratification can be assigned and adjusted when results are available.

MRD positivity is defined as detectable disease by the most sensitive method used for each patient. In some cases this will be limited to flow cytometry. PCR and deep-sequencing MRD may also define MRD positivity in patients for whom these tests are available.

5.2.2 First BM and PB chimerism tests are due at Day +28 but can be done between Day +21 and Day +42 when ANC >500 x 3 days.

- A minimum of 8 ml of each BM and PB in ACD tube will be sent to the UCSF or local Immunogenetics clinical laboratory for chimerism testing.

5.2.3 When available locally, whole blood chimerism and subset (CD3, CD14/15, and CD19) chimerism will be tested and prioritized according to underlying disease:

- For T-cell malignancy: CD3 > CD14/15
- For B-cell malignancy: CD3 > CD19 > CD14/15
- For myeloid malignancy: CD3 > CD14/15

5.2.4 Bone marrow subset chimerism will be similarly prioritized:

- For T-cell malignancy: CD34 > CD3
- For B-cell malignancy: CD34 > CD19 > CD3
- For myeloid malignancy: CD34 > CD33 > CD3

5.2.5 If PB converts to FDC, BM must be obtained for chimerism prior to starting the next cycle in order to determine eligibility for further DLI.

Time point	Required Study	Comments
Day +21 through Day +42	PB Chimerism PB MRD* BM Chimerism BM MRD	Required prior to Cycle 1 (Aza alone)
2-8 weeks following completion of withdrawal of immunosuppression.	PB chimerism PB MRD*	Required prior to Cycle 2 (Aza +/- DLI)
4-8 weeks following initiation of Cycle 2	PB Chimerism PB MRD* BM chimerism	Required prior to Cycle 3 (Aza +/- DLI)

Time point	Required Study	Comments
	BM MRD	
4-8 weeks following initiation of Cycle 3	PB chimerism PB MRD*	Required prior to Cycle 4 (Aza +/- DLI)
4-8 weeks following initiation of Cycle 4	PB chimerism PB MRD* BM chimerism BM MRD	Required prior to Cycle 5 (Aza +/- DLI)
4-8 weeks following initiation of Cycle 5	PB chimerism PB MRD*	Required prior to Cycle 6 (Aza +/- DLI)
4-8 weeks following initiation of Cycle 6	PB chimerism PB MRD* BM chimerism BM MRD	Required prior to Cycle 7 (Aza +/- DLI)

Table 1: Schedule of chimerism and MRD analysis for each cycle. PB DS-MRD is recommended for ALL patients when available. May omit PB MRD if concurrent BM MRD sample is sent. Peripheral blood MRD by flow cytometry as clinically indicated.

5.3 Risk Stratification

- 5.3.1 Risk is evaluated and assigned prior to each azacitidine cycle based on clinical testing specific to that patient's disease.
- 5.3.2 For patients with MDS, any evidence of disease may be used to stratify the patient accordingly. In the absence of evidence of persistent disease, chimerism will be used to stratify the patient. MDS patients with no evidence of disease and 100% chimerism will be stratified as standard risk.
- 5.3.3 Peripheral blood disease assessment will be done as clinically indicated. Peripheral blood MRD by deep sequencing (if positive) may be used to risk-stratify ALL patients instead of bone marrow MRD. Any evidence of disease in peripheral blood for patients with AML/JMML or MDS will prompt BM evaluation as clinically indicated. In this instance, study treatment may continue after BM evaluation is complete.
- 5.3.4 Risk stratification criteria:
 - Low Risk
 - May only be applied to acute lymphoblastic leukemia patients
 - All of the following
 - Pre-transplant deep sequencing MRD negative, AND
 - All post-transplant deep sequencing MRD samples negative, AND
 - Any chimerism or GVHD status
 - ALL patients with negative deep-sequencing MRD pre- and post-transplant will be treated as low-risk regardless of chimerism
 - Standard Risk
 - Active Grade I GVHD, OR
 - Any history of Grade II (or higher) GVHD, OR
 - All of the following
 - Full Donor Chimerism AND
 - Pre-HSCT MRD $<10^{-5}$ (bone marrow) AND
 - Post-HSCT MRD $<10^{-5}$ (bone marrow), unless 3-fold increase is observed
 - High Risk
 - No active acute or chronic GVHD, AND
 - No history of Grade II (or higher) acute GVHD or chronic GVHD, AND

- Any of the following:
 - Mixed chimerism OR
 - Pre-HSCT MRD $> 1 \times 10^{-5}$ OR
 - Post-HSCT MRD at day 28 or later $\geq 10^{-5}$ once, OR
 - Post-HSCT MRD at day 28 or later $\geq 10^{-6}$ with ≥ 3 -fold increase on any subsequent measurement (need not be consecutive).
 - Post-HSCT MRD $< 1 \times 10^{-5}$ is treated as Standard Risk until a 3-fold increase is documented.

5.4 Chimerism assessment

5.4.1 Chimerism assessment will be done at the UCSF Immunogenetics and Transplantation Laboratory [REDACTED], or at the local institution for collaborating sites. Chimerism will be assessed using short tandem repeats (STR) on whole blood and bone marrow and on cell subsets when such testing is available. Peripheral blood subset analyses will include whole blood CD3+, and CD14/15 subsets for all patients. Patients with B-cell malignancies will also have CD19+ subset tested. For bone marrow specimens, CD34+ will also be analyzed in all patients, in addition to disease-specific subsets.

5.4.2 Patients with any degree of host chimerism detected in any subset from either peripheral blood or bone marrow will be considered high risk.

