5.5 Criteria for standard or fast withdrawal of immunosuppression (SWI versus FWI)

5.5.1 GVHD, MRD, and chimerism status must be assessed prior to each cycle and applied to risk stratification as above.

5.5.2 If the patient meets High-Risk criteria, then fast withdrawal of immunosuppression (FWI) will be initiated as early as Day +30.

5.5.3 If patient meets Standard-Risk criteria (or Low-Risk criteria for ALL patients), standard withdrawal of immunosuppression (SWI) will be initiated.

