- Azacitidine without DLI: Patients meeting Standard Risk criteria will receive azacitidine without DLI at a dose of 40mg/m² IV or SC x 4 days every 6 weeks. DLI should be considered for patients with resolved Grade 2 GHVD if pre- or post-transplant MRD is positive.
- Azacitidine with DLI: Patients meeting High Risk criteria, who also have available cells, will receive DLI in addition to azacitidine. Patients with history of Grade 2 GVHD (which has resolved) may also receive DLI if pre- or post-transplant MRD is positive at the discretion of the treating physician.
 - Administration of azacitidine following withdrawal of immunosuppression will commence (typically on a Monday) 2-8 weeks following *completion* of SWI/FWI (see section 6.2 for dose adjustments).
 - Azacitidine will be given at a dose of 40mg /m² IV or SC daily for 4 days every 6 weeks.
 - Escalating doses of DLI will be administered (typically on a Friday) within 5 days following the last dose of azacitidine every cycle (see section 5.8 for DLI schedule).
 - For patients with negative pre- and post-transplant MRD:
 - Once MDC resolves to FDC in both blood and bone marrow, DLI will be discontinued and patient will continue to receive azacitidine alone for a maximum of 7 cycles as tolerated.
 - If FDC is detected in blood, bone marrow chimerism must be obtained and confirmed to be mixed before proceeding with DLI.
- If DLI is administered without azacitidine during cycles 2 through 7, the subject should continue with all subsequent study assessments, but will be analyzed separately with regard to safety and efficacy.
- Cycles may be delayed for reasons such as toxicity, as per dose adjustment section 6.0.
- For all patients who receive azacitidine, a total of 7 cycles may be administered as tolerated.

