5.8.2 Mixed Chimerism

- Patients with persistent MDC following withdrawal of immunosuppression will receive DLI with the next cycle of azacitidine. Mixed chimerism of low purity should be repeated before proceeding with DLI and/or FWI in order to ensure mixed chimerism. If MDC persists after cycle 7, DLI may be administered without azacitidine after discussion with the study chair.
- Patients who revert to MDC on subsequent PB or BM testing will receive DLI with the next cycle of azacitidine.
- Patients with FDC are generally not eligible for further DLI except as described below.

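### For an MRD-negative patient with mixed chimerism and resolved Grade II GVHD, 5.8.2 orders DLI while 5.3.4 and 5.7.6 give azacitidine alone, and no text says which prevails

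*Combined protocol and SAP*

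**What the plan says.** Two sections act on chimerism alone.

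- Section 5.4.2: "Patients with any degree of host chimerism detected in any subset from either peripheral blood or bone marrow will be considered high risk".
- Section 5.8.2, under the criteria for DLI: "Patients with persistent MDC following withdrawal of immunosuppression will receive DLI with the next cycle of azacitidine", and "Patients who revert to MDC on subsequent PB or BM testing will receive DLI with the next cycle of azacitidine".

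Three sections act on the full risk criteria, which include GVHD history.

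- Section 5.3.4 lists as sufficient for Standard Risk: "Any history of Grade II (or higher) GVHD, OR". It lists as necessary for High Risk: "No history of Grade II (or higher) acute GVHD or chronic GVHD, AND". Mixed chimerism counts toward High Risk only once that condition is met.
- Section 5.7.6: "Patients meeting Standard Risk criteria will receive azacitidine without DLI". It mentions resolved Grade 2 GVHD twice, and each time makes DLI possible only if pre- or post-transplant MRD is positive.
- Section 5.5.3: "If patient meets Standard-Risk criteria (or Low-Risk criteria for ALL patients), standard withdrawal of immunosuppression (SWI) will be initiated". Section 5.5.2 gives the fast taper to patients who meet the High-Risk criteria.

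**The concern.** A clinician who opens the DLI section finds an unconditional order to infuse. One who opens the risk criteria and the treatment schedule finds that the same patient gets azacitidine alone. Both are worded as rules, and three institutions have to apply them.

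The stakes are safety and consistency. Section 9.1 warns that DLI raises the risk of severe and potentially fatal GVHD. Grade III/IV acute GVHD is a primary safety endpoint (8.3.2). Appendix 3 (5.1.4) advises caution with DLI in patients who have had acute GVHD; it is written for DLI outside a study, although 6.1 refers to it for toxicity management. The choice also decides who enters the DLI subset in 8.7.3, whose GVHD rates can suspend enrollment and further DLI.

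**Working it through.** The plan gives no figure to reproduce, so the check applies the rules to one profile: AML, resolved Grade II acute GVHD, mixed chimerism, MRD negative before and after transplant, DLI cells available.

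**1. The two routes**

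| Step | Chimerism route | Risk-criteria route |
|---|---|---|
| Risk label | 5.4.2: high risk | 5.3.4: Standard Risk; the High Risk list is not met |
| DLI | 5.8.2: given with the next azacitidine cycle while chimerism is mixed | 5.7.6: azacitidine without DLI; the Grade 2 exception needs positive MRD |
| Taper | 5.5.2: fast, but only if the 5.4.2 label counts as meeting the High-Risk criteria | 5.5.3: standard |

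The DLI row is a direct conflict, because 5.8.2 does not pass through a risk class. The taper row is conditional, because neither 5.4.2 nor 5.8.2 orders a fast taper.

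**2. Who is affected**

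- ALL that is deep-sequencing negative throughout is outside the conflict: 5.3.4 makes it Low Risk whatever the chimerism or GVHD status.
- Suspected or active GVHD is outside it: 6.1 stops DLI and withdrawal of immunosuppression. Grade III-IV GVHD is dealt with in 3.1.2 and the Figure 1 captions.
- Patients without available cells are outside the DLI conflict (3.1.4, 3.2.1.1, 5.7.6).
- If MRD is positive, 5.7.6 allows DLI after resolved Grade 2 GVHD, so the direct DLI clash is confined to negative MRD. The conditional taper conflict is not, since 5.5.2 and 5.5.3 depend on risk group only.

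**3. Search for a rule of precedence**

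- Section 5.5.1: "GVHD, MRD, and chimerism status must be assessed prior to each cycle and applied to risk stratification as above". This follows both 5.3.4 and 5.4.2 and ranks neither.
- Section 3.1.4 ties DLI to the High Risk criteria, and the schema High Risk box admits only no GVHD or resolved Grade I. Both agree with 5.3.4, but neither makes 5.8.2 subject to it.
- Section 9.5 says that MRD-negative (Standard-Risk) patients will not receive DLI. It leans the same way but cannot settle the case: under 5.3.4, MRD-negative mixed chimerism without GVHD is High Risk, and 5.7.6 has rules for stopping DLI in MRD-negative patients.
- Section 5.3.2 leans the other way for MDS: without evidence of persistent disease, chimerism is used to stratify.

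No sentence ranks the two routes.

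**4. Size per affected patient**

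- DLI: 7 cycles − 1 (cycle 1 is azacitidine alone) = at most 6 infusions, against 0. DLI after cycle 7, which 5.8.2 permits after discussion with the study chair, is not counted.
- Cell dose at that ceiling, matched related donor (5.9.2): 1×10⁷ + 5 × (5×10⁷) = 2.6×10⁸ CD3+ cells/kg, against 0.
- Taper, if that conflict arises: suggested 10 weeks (5.6.1) against 2 to 4 weeks (5.6.2). 10 − 4 = 6 and 10 − 2 = 8, so 6 to 8 weeks shorter.

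**The case against.** The best reply is that neither chimerism rule can be read in isolation. Taken literally, 5.4.2 would make Low Risk ALL with mixed chimerism high risk, and 5.8.2 would order DLI during active GVHD or without cells. Everyone reads in limits from other sections there. The same reading, with 5.3.4 as the section that sets the risk criteria, resolves this patient too. On this view 5.4.2 is a loose sentence in a section about testing, and only a cross-reference is missing.

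Much of that stands. The probable intent is that 5.3.4 governs. The phrase in 5.5.2 most naturally refers to 5.3.4, so the taper conflict is weak.

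It does not dispose of the DLI conflict. In the comparison cases the limit is written down: 5.3.4 overrides chimerism for Low Risk ALL, 6.1 overrides chimerism and MRD status for suspected GVHD, and 3.2.1.1 covers insufficient product. No such override exists for a history of Grade II GVHD. There, one section orders DLI, another orders azacitidine without it, and the reader must infer which was meant.

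A reader might also infer that 5.4.2 and 5.8.2 themselves direct a fast taper, or that the plan mandates a taper 6 to 8 weeks shorter. The text supports neither. The taper follows only through 5.5.2, and both schedules are suggestions under institutional procedure. That half also needs Grade II GVHD to have begun and resolved by the start of taper, suggested for day 30-50.

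**Conclusion.** The conflict over DLI is real. As written, 5.8.2 would give DLI to a patient whom 5.3.4 excludes from High Risk and to whom 5.7.6 gives azacitidine alone. This is a wrong rule as written, not missing detail, and it should be corrected. The taper conflict is secondary and conditional.

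The size is bounded, not estimated. Six infusions is a ceiling: it needs mixed chimerism through every cycle, enough cells, and no suspected GVHD. The number of affected patients is unknown. A reader might take the 20-35% rate of Grade III-IV acute GVHD after DLI in 8.7.3 as the excess risk here. The documents do not support that, because it is a general published range and not specific to patients with resolved Grade II GVHD.

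The conclusion assumes the profile described: GVHD resolved at Grade II, mixed chimerism, negative MRD before and after transplant, not Low Risk ALL, and cells available.

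**What to change.** Say in words that 5.3.4 governs.

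1. End the 5.4.2 sentence with: *will be considered to have mixed chimerism and will be stratified per 5.3.4*.
2. Limit both DLI sentences in 5.8.2 to patients who meet the 5.3.4 High Risk criteria, and keep the 5.7.6 discretion for resolved Grade 2 GVHD with positive MRD.

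The first change also removes any basis for a fast taper on the 5.4.2 label alone. The cost is protocol wording only; sample size and analysis are unchanged.
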